ClinicalTrials.gov number	ClinicalTrials.gov Identifier: NCT03158051
Phase	not applicable
Methodology	Randomized controlled Trial
Study Duration	5 years
Study Center(s)	Two Healthcare Systems - UW Health (Madison, WI) - Aurora Health Care (Milwaukee, WI)
Objectives	
Aim 1. To evaluate the effect of MyHEART (home blood pressure monitor distribution and health coaching) on clinical outcomes, the change in systolic and diastolic blood pressure (primary) and hypertension control (secondary) after 6 and 12 months, compared to usual clinical care. We hypothesize that MyHEART will significantly decrease systolic and diastolic blood pressures (clinic and 24-hour ambulatory) in young adults, compared to usual clinical care.
 
Aim 2. To evaluate the effect of MyHEART on hypertension self-management behavior (behavioral outcomes) at 6 and 12 months, compared to usual clinical care. We hypothesize that MyHEART will increase the frequency of home blood pressure monitoring and lifestyle modifications (increased physical activity, decreased sodium intake).
 
Aim 3. To examine whether MyHEART's effects on self-management behavior are mediated through variables of perceived competence, autonomy, motivation, and activation (mediation outcomes). Based on our pilot study and theoretical framework, we hypothesize that MyHEART's effects will be mediated through perceived competence, autonomy, internal motivation, and patient activation.

Number of Subjects	N=340
Diagnosis	uncontrolled hypertension
Main Inclusion Criteria	18-39 years with a diagnosis of "elevated blood-pressure reading, without diagnosis of hypertension" or a hypertension diagnosis, uncontrolled blood pressure ($\geq 140/90$ mmHg), and medically homed at one of the included clinical sites
Main Exclusion Criteria	Any of the following diagnoses: chronic kidney disease, congestive heart failure, sickle cell anemia, cystic fibrosis, stroke, myocardial infarction, coronary artery revascularization, or prior/planned organ transplant; inability to provide informed consent or read or communicate in English; residence at skilled nursing or correctional facility; prescription of warfarin, novel oral anticoagulant, planned chemotherapy, planned radiation therapy, plan to move out of area in next 6 months; pregnant or plan to become pregnant in next year; illegal drug use other than marijuana in past 30 days; syncope in past 12 months

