Study Product, Dose, Route, Regimen	Health coach face-to-face visits, with follow-up telephone calls, self-management support, and primary care provider feedback
FDA status of product	not applicable

Duration of administration	6-month intervention; 6-month maintenance evaluation (12-month total follow-up)
Reference therapy	Usual Clinical Care
Statistical Methodology	The primary comparisons for the co-primary outcomes of systolic and diastolic blood pressure change from baseline to 6 months will be done using analysis of covariance with MyHEART and baseline blood pressure as independent covariates. The primary comparisons for the secondary outcome of hypertension control will be based on Fisher's exact tests. Mediation analysis will be performed for Aim 3.

Schematic of Study Design

Figure: Eligibility, Enrollment, Randomization, Follow-up and Analysis

Contents

Study Summary.....	6
1 Key Roles.....	12
2 Background and Introduction.....	12
2.1 Background and Rationale.....	13
2.1.1 Development of MyHEART.....	13
2.2 Hypothesis.....	14
2.3 Study Agent.....	14
2.4 Summary of Clinical Data.....	15
2.5 Potential Risk and Benefits to Subjects.....	16
2.5.1 Known Potential Risks	16
2.5.2 Alternative to Study Participation	17
2.5.3 Protection Against Risks	17
2.5.4 Adverse Event Reporting	19
2.5.5 Potential Benefits to the Subjects	20
2.5.6 Risk Minimization	20
3 Study Design and Endpoints.....	21
3.1 General Design	21
3.1.1 Primary Study Endpoints.....	22
3.1.2 Secondary Study Endpoints.....	22
3.1.3 Primary Safety Endpoints.....	22
4 Study Subjects – Enrollment and Withdrawal.....	22
4.1 Subject Population	22
4.2 Inclusion Criteria.....	23
4.3 Exclusion Criteria	23
4.4 Subject Screening for Recruitment	24
4.4.1 Subject Identification	24
4.4.2 Recruitment and Retention Strategies	24
4.5 Vulnerable Populations	25
4.5.1 Subject Capacity	25
4.5.2 Subject/Representative Comprehension	25
4.6 Informed Consent.....	26
4.6.1 Process of Consent.....	26
4.6.2 Consent Form.....	26
4.6.3 HIPAA.....	26
4.6.4 Revoking Consent.....	27
4.6.5 Costs to the Subject	27
4.6.6 Payment for Participation	27
4.7 Early Withdrawal of Subjects	27

4.7.1	Premature termination of study	27
4.7.2	When and How to Withdraw Subjects.....	28
4.7.3	Data Collection and Follow-up for Withdrawn Subjects.....	28
5	Study Procedures	28
5.1	Prior and Concomitant Therapy	28
5.2	Randomization and Blinding of Intervention	28
5.3	Established Standard of Care	29
5.4	Study Visits.....	29

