3.1.2 Secondary Study Endpoints

- Hypertension Control: Percentage of participants that achieve hypertension control at 6 months. Hypertension control will be defined using ambulatory blood pressures as the gold standard (<130/80 mmHg); otherwise a clinic blood pressure of <140/90 mmHg will be used.
- Change in hypertension self-management behavior at 6 and 12 months compared to usual care
 - Dietary Changes (Automated Self-Administered 24-hour Dietary Assessment)
 - Change in physical activity (Godin Physical Activity Questionnaire)
 - Home Blood Pressure Monitoring Frequency¹²⁴
 - Change in weight (kg)
 - Change in body mass index (BMI, kg/m²)
- Change in perceived competence, autonomy, and motivation
 - Perceived Competence – Perceived Competence Scales (PCS)
 - Perceived autonomy/support from medical team - Health-Care Climate Questionnaire (HCCQ)
 - The Degree to which a person's motivation for a behavior is autonomous or self-determined: Treatment Self-Regulation Questionnaires (TSRQ)
 - Health Coach Fidelity

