5.2 Randomization and Blinding of Intervention

Randomization assignments for both sites will be generated by the UW Biostatistics Clinical Trials Statistical Data Analysis Center stratified by research site, in block sizes of 4 and 6 to ensure equal allocation. The Research Electronic Data Capture (REDCap) clinical data management system will be used to verify eligibility and data completeness prior to randomization. The UW Biostatistics team will develop a randomization list, which will be provided to the MyHEART research staff in a binder. There will be two people responsible for the binder at all times at HIP (PI and research manager) who will give the randomization assignment upon receiving a phone call from the

research assessor (from either site) conducting Visit 2. Until the staff receives a phone call, the binder will remain in a locked file cabinet, separate from other research materials, within a locked office at [name] (HIP).

All study participants will have contact with research staff (e.g., research coordinators, research visit study assessment staff). To reduce bias, MyHEART 6- and 12-month assessors will be blinded to treatment assignments.¹³⁰ Assessors will be trained to treat patients in both study groups identically per protocol.¹³¹ Ambulatory monitoring will be the gold standard for blood pressure measurements.

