Blood pressures at each research site will be assessed with a Dinamap Monitor. Cuff size will be determined by arm circumference. An appropriate sized¹⁶⁶ blood pressure cuff will be connected to an automated sphygmomanometer (Dinamap). Each site will have the following cuff sizes available: small adult (for arm circumference of 22-26 cm), regular adult (27-34 cm), and large adult (35-42 cm). A blood pressure measurement will be obtained on the right upper arm, then the left upper arm, for the initial assessment. Right arm blood pressures will be subsequently used for the initial and follow-up visits, unless the left arm systolic blood pressure is ≥10 mmHg higher. The average of the second and third systolic and diastolic pressures, each taken 1 minute apart, will define the baseline clinic blood pressure.¹⁶⁷ If a participant's upper arm is too large, a forearm blood pressure will be obtained. All participants (intervention and control) will receive copies of their baseline, 6-month, and 12-month research clinic blood pressures to share with their usual healthcare provider, and will receive instructions on recommended primary care clinic follow-up.^{43,168}

24-Hour Blood Pressure Monitoring:¹⁶⁹⁻¹⁷¹ 24-hour blood pressure monitoring will take place at baseline, 6 months, and 12 months. Staff trained in the use of the 24-hour ambulatory blood pressure monitor will apply the appropriate sized cuff to the subjects' non-dominant arms unless the systolic blood pressure difference as measured during the clinic blood pressure assessment is >10 mmHg, in which case the arm with the highest value obtained

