6.2 Statistical Methods

See Appendix for the full Statistical Analysis Plan (SAP)

Statistical Analysis Plan Overview:

Data will be analyzed by intent to treat. Missing data will be imputed using multiple imputations.

For Aim 1, the comparisons for the primary outcomes of systolic and diastolic blood pressure change from baseline to 6 months will be done using analysis of covariance. The primary comparisons for the secondary outcome of hypertension control at 6 months will be based on Fisher's exact tests. Sequential hypothesis testing will also be performed. The 12-month analysis will focus on *maintenance* of behavior change, to assess whether significant differences seen between baseline and 6 months are retained. We will also assess the differential effectiveness of the intervention across subgroups by developing exploratory regression models.

For Aim 2, behavioral outcomes will be analyzed in a similar manner as with the clinical outcomes in Aim 1 depending on whether they are continuous or categorical. Analyses (t-tests or Wilcoxon tests and ANCOVA for continuous variables; Fisher's exact test for the categorical variable) will be performed for differences from baseline to 6 months between treatment groups. Linear or generalized linear mixed-effects regression models will be fit to describe longitudinal behavioral measurements over time.

For Aim 3, analyses will examine hypothesized mediators of the MyHEART intervention (for example, autonomy support, internal motivation, perceived competence, and patient activation). We will estimate mediation effects in multilevel models¹⁸⁶⁻¹⁹⁰ where mediation is assessed by fitting two models. Standard errors and 95% confidence intervals for the mediation effect and percent-mediated estimates will be calculated. This analysis will be pivotal to guide future replication and dissemination of MyHEART.

6.3 Planned Interim Analysis:

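### Six-month hypertension control is compared by an unadjusted Fisher's exact test; adjusting for baseline pressure and site would be a cheap gain in precision, unless the unsupplied SAP appendix already does so

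*Combined protocol and SAP*

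**What the plan says.** Section 6.2 (Statistical Methods): "The primary comparisons for the secondary outcome of hypertension control at 6 months will be based on" Fisher's exact tests. The Study Summary, under Statistical Methodology, agrees: "The primary comparisons for the secondary outcome of hypertension control will be based on" the same test. Neither place mentions a covariate or site.

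The co-primary pressures are treated differently. The Study Summary analyses them by "analysis of covariance with MyHEART and baseline blood pressure as independent covariates".

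The Objectives list "hypertension control (secondary) after 6 and 12 months" as the secondary clinical outcome of Aim 1. Section 3.1.2 defines it as "Percentage of participants that achieve hypertension control at 6 months", judged on ambulatory pressure (<130/80 mmHg) or, failing that, clinic pressure (<140/90 mmHg).

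The covariates exist. Allocation is "stratified by research site, in block sizes of 4 and 6 to ensure equal allocation" (section 5.2). Under section 5.4, the mean of readings two and three "will define the baseline clinic blood pressure", and "24-hour blood pressure monitoring will take place at baseline, 6 months, and 12 months".

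Sections 4.7.3 and 6.2 call for multiple imputation. The overview gives no rule for combining Fisher p-values across imputed data sets. It refers to a full SAP in an appendix, which is not among the documents supplied. The only other regression models it mentions for Aim 1 are exploratory subgroup models.

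**The concern.** Control is a cut-off applied to the same pressures that the co-primary analysis adjusts for baseline. On the text supplied, the plan uses baseline pressure in one analysis and drops it in the other. At stake is precision on the secondary clinical outcome of Aim 1: lower power and a wider interval than the collected data allow. A smaller matter is that the ANCOVA, as summarised, also leaves out site.

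**Working it through.** **1. The plan's own figures (section 6.1).** Inputs: 264 evaluable, so 132 per arm; differences 6.3 and 4.0 mmHg; SDs of change 13.6 and 9.7; two-sided 0.025 each (z = 2.241).

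- SBP: SE = 13.6 x sqrt(2/132) = 1.674; 6.3/1.674 = 3.763; power = Phi(3.763 - 2.241) = 0.936 (stated 0.94).
- DBP: SE = 9.7 x sqrt(2/132) = 1.194; 4.0/1.194 = 3.350; power = Phi(3.350 - 2.241) = 0.866 (stated 0.87).

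Both reproduce. No power is stated for hypertension control. Since 340 x 0.85 = 289 while 264/340 implies 22.4% loss, both loss rates are used in step 4.

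**2. Fisher's true size.** The exact calculation at 132 per arm and nominal two-sided 0.05 gives 0.0358, 0.0373, 0.0368 and 0.0382 at control rates of 20%, 30%, 35% and 40%. For an assumed 35% v 50%, power is 0.662, against 0.695 for the unadjusted normal-approximation test.

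**3. Effect of the baseline correlation r.** Simulation with n = 264, complete data and 2,000 trials per row. Assumed: about 39% control in usual care, SBP-DBP correlation 0.6, no site effect, alpha 0.05. The SDs in section 6.1 are SDs of change, so the follow-up SD is SD of change / sqrt(2(1 - r)). For SBP at r = 0.3 this is 13.6/sqrt(1.4) = 11.5, and at r = 0.7 it is 13.6/sqrt(0.6) = 17.6.

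| r | Effect | Fisher | Chi-square | Adjusted logistic | Gain over Fisher (points) |
|---|---|---|---|---|---|
| 0.3 | full | 0.9370 | 0.9490 | 0.9530 | 1.6 |
| 0.3 | 60% | 0.5505 | 0.5995 | 0.6095 | 5.9 |
| 0.5 | full | 0.8305 | 0.8610 | 0.8990 | 6.9 |
| 0.5 | 60% | 0.3995 | 0.4420 | 0.4955 | 9.6 |
| 0.7 | full | 0.6060 | 0.6530 | 0.7845 | 17.9 |
| 0.7 | 60% | 0.2660 | 0.3105 | 0.3955 | 13.0 |

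Under no effect, Fisher rejects in 0.034-0.039 of trials and adjusted logistic in 0.049-0.055. A separate run at n = 264 agrees. At r = 0.5 it gives 0.84 v 0.90 at the design effects and 0.57 v 0.67 at three quarters of them; at r = 0.3 and the design effects it gives 0.94 v 0.96.

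**4. Missing data and imputation, r = 0.5.** Simulation with 340 randomised and 3,008 trials. Assumed: two equal sites differing by 0.3 SD, 35% control in usual care, SBP-DBP correlation 0.6, one measurement modality, missingness depending on baseline pressure, 20 imputations, alpha 0.05. Power at 15% / 22.4% loss:

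| Analysis | Design effects | Three quarters |
|---|---|---|
| Fisher, observed cases | 0.863 / 0.830 | 0.626 / 0.592 |
| Chi-square, observed cases | 0.877 / 0.845 | 0.645 / 0.619 |
| Logistic, baseline only, observed | 0.918 / 0.891 | 0.722 / 0.690 |
| Logistic, baseline and site, observed | 0.924 / 0.895 | 0.732 / 0.699 |
| Same model, imputed, Rubin's rules | 0.931 / 0.917 | 0.734 / 0.716 |
| Imputed Fisher, mean p | 0.878 / 0.857 | 0.638 / 0.610 |
| Imputed Fisher, median p | 0.905 / 0.896 | 0.681 / 0.670 |

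- Pooled model less observed-case Fisher: 6.8, 8.7, 10.8 and 12.4 points.
- Pooled model less median p: 2.6, 2.1, 5.3 and 4.6 points.
- Pooled model less mean p: 5.3, 6.0, 9.6 and 10.6 points.
- Steps within the gain: replacing Fisher by chi-square 1.4-2.7 points, baseline pressure 4.1-7.7, site 0.4-1.0, imputation 0.2-2.2.
- The 95% CI half-width for the risk difference falls from 0.112/0.118 to 0.102/0.106, which is 9-10% narrower.
- Size under no effect: Fisher 0.039/0.040; adjusted logistic on observed cases 0.051/0.055; pooled 0.036/0.034; mean p 0.028/0.026; median p 0.038/0.039.

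At r = 0.3 with the change SDs held fixed, 22.4% loss and design effects (1,000 trials), Fisher has 0.935, median p 0.960 and the pooled model 0.967. The gain over median p is then 0.7 points.

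**5. ANCOVA without site.** With equal sites and r = 0.5, the SE is overstated by sqrt(1 + 0.25 d^2/0.75) - 1, where d is the site difference at follow-up in SDs. This is 1.5% at d = 0.3, 4.1% at d = 0.5, and zero if the sites do not differ.

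**The case against.** The strongest reply is that nothing is wrong: a simple, assumption-free test on a secondary endpoint is a legitimate choice. That stands, and it limits this point to efficiency.

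Second, the larger gains are measured against observed-case Fisher, while the documents plan imputation. This also stands. Against median-p combination little remains, and at a correlation of 0.3 almost nothing. A low correlation is plausible: people with white coat hypertension are excluded (section 4.3), which narrows the baseline range, and antihypertensive treatment may change during follow-up (section 5.1).

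Third, a reader might infer that choosing Fisher rules out a pooled estimate. It does not. An unadjusted risk difference has a standard error and can be pooled by Rubin's rules alongside the test. The case for a model must rest on the precision from baseline adjustment.

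Fourth, the pooled model is itself conservative in simulation (0.036/0.034), so correcting Fisher's size is not the main argument. At a correlation of 0.3, however, most of the small gain over observed-case Fisher does come from leaving Fisher's conservatism: in step 3, chi-square already recovers 1.2 of 1.6 and 4.9 of 5.9 points.

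Finally, the appendix may already specify an adjusted model, a pooling rule and the full covariate list. That cannot be checked here.

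**Conclusion.** The point holds as an optional improvement, subject to the SAP appendix. With a baseline correlation of 0.5, adjustment gains about 6-12 points of power over observed-case Fisher and about 2-5 over imputed Fisher combined by median p. At 0.3 the figures are about 2-6 points and essentially nil; at 0.7 the gain is larger. Of what the covariates add, nearly all comes from baseline pressure. Site adds at most about 1 point and imputation 0-2.

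These figures rest on assumed control rates, correlations, site difference and alpha. The conclusion that depends least on them is qualitative: the covariates are already collected, and the plan already uses baseline pressure for the co-primary outcomes.

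A reader might infer that the planned test is invalid or inflates type I error. The documents do not support that: Fisher's test is conservative here, and omitting site from the ANCOVA is at worst slightly conservative too.

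**What to change.** - Make the main comparison of 6-month control a logistic regression on arm, baseline SBP, baseline DBP and site. Report a marginal (standardised) risk difference with 95% CI, pooled by Rubin's rules.
- Name the baseline pressure that enters the model. Clinic pressure is one option, since it does not depend on completing ambulatory monitoring, which section 5.4 does not require for enrolment.
- Impute the 6-month pressures, stating which modality is imputed, and derive control by the rule in section 3.1.2.
- Include site in the imputation model and in the SBP and DBP ANCOVA.
- Keep observed-case Fisher as a sensitivity analysis.
- If the SAP appendix already specifies this, align the Study Summary and section 6.2 with it.

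The cost is a few lines of SAP text and programming, with no new data. Fisher's strict size guarantee is given up, and the pooled result depends on the imputation model; the retained Fisher analysis is the check on both.

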2.2 Hypothesis

Aim 1. To evaluate the effect of MyHEART (home blood pressure monitor distribution and health coaching) on clinical outcomes, the change in systolic and diastolic blood pressure (primary) and hypertension control (secondary) after 6 and 12 months, compared to usual clinical care. **We hypothesize** that MyHEART will significantly decrease systolic and diastolic blood pressures (clinic and 24-hour ambulatory) in young adults, compared to usual clinical care.

Aim 2. To evaluate the effect of MyHEART on hypertension self-management behavior (behavioral outcomes) at 6 and 12 months, compared to usual clinical care. **We hypothesize** that MyHEART will increase the frequency of home blood pressure monitoring and lifestyle modifications (increased physical activity, decreased sodium intake).

Aim 3. To examine whether MyHEART's effects on self-management behavior are mediated through variables of perceived competence, autonomy, motivation, and activation (mediation outcomes). Based on our pilot study and theoretical framework, **we hypothesize** that MyHEART's effects will be mediated through perceived competence, autonomy, internal motivation, and patient activation.

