- **Social Support** will be evaluated using a brief multi-dimensional evaluation validated for patients' chronic illnesses (example: The Medical Outcomes Study Social Support Survey).^{149,160-162}
- **Global medication adherence** will be assessed using the Morisky adherence scale.^{163,164}

Baseline Electronic Health Record and Other Database Data Collection

- **Healthcare utilization** will be evaluated using the John Hopkins Adjusted Clinical Group Case-Mix System, which assesses morbidity burden based on patient age, gender, and patterns of disease,^{50,60,66,165} the number of clinic visits will be measured.
- **Baseline antihypertensive medications and other medications:** Number of antihypertensive medication classes will account for varying hypertension treatment at baseline. Data will be acquired from the electronic health record and participant self-report, and will include prescription and non-prescription medications.
- **Primary care provider characteristics** (age, gender, specialty, time since completed medical school, % of panel with hypertension, panel size) will be obtained when available from the electronic health record and/or the American Medical Association Masterfile data.^{50,60}

Interviewer-Administered Data Collection (Baseline, 6 months, and 12 months)

- **Physical Activity.** We will assess physical activity using the Godin Exercise Questionnaire to evaluate weekly leisure activity and total leisure activity.
- **Automated Self-Administered 24-Hour (ASA24) Dietary Assessment Tool** – A web-based tool that enables multiple, automatically coded, self-administered 24-hour recalls. This tool will be used to assess, for example, sodium, fruit, and vegetable intake in relation to the DASH-sodium diet.

Blood Pressure Measurements

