6.1 Sample Size Determination

For Aim 1, approximately 930 individuals will be screened to get to a total of 340 enrolled participants (170 participants per randomized arm). This is designed under the assumption that there will be a further 15% dropout rate at the 6-month mark following randomization, to result in an effective sample size of 264.¹⁸⁴ In Nidich et al.,¹⁸⁵ the 3-month transcendental meditation program showed a mean difference of 6.3 and 4.0 in systolic and diastolic blood pressure change with a standard deviation of 13.6 and 9.7, respectively, as compared to a case of usual control among young adults at hypertension risk. With an effective sample size of 264, there is power of 0.94 and 0.87 for systolic and diastolic blood pressure, respectively, each at a two-tailed 0.025 test for an overall significance level of 0.05. For Aim 2, the effective sample size of 264 subjects will provide 90% power to detect a difference in the population mean difference from baseline to 6 months between treatment groups of about 0.4 standard deviations of the differences (moderate effect size). Aim 3 is an exploratory aim.

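### Aim 2's categorical behaviour outcome is tested with Fisher's exact test, which cannot adjust for baseline or site; if the outcome is ordinal, the test also ignores order and direction

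*Combined protocol and SAP*

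**What the plan says.** Section 6.2 is an overview that refers to an appendix for the full SAP; that appendix is not among the documents. For Aim 2 it plans t or Wilcoxon tests plus ANCOVA for continuous measures, and "Fisher's exact test for the categorical variable". These analyses "will be performed for differences from baseline to 6 months between treatment groups". The categorical variable is in the singular and is not named. The next sentence adds: "Linear or generalized linear mixed-effects regression models will be fit to describe longitudinal behavioral measurements over time".

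Section 6.2 also says that Aim 2 follows the approach of Aim 1. The Study Summary specifies the Aim 1 ANCOVA with arm and baseline value as covariates.

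Section 3.1.2 lists the behaviour endpoints as diet, physical activity, "Home Blood Pressure Monitoring Frequency", weight and BMI, with no response scale for monitoring frequency. Section 5.4 measures activity with the "Godin Exercise Questionnaire to evaluate weekly leisure activity and total leisure activity" and does not say whether the result is a score or a band.

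The Aim 2 hypothesis in Section 2.2 is directional: "MyHEART will increase the frequency of home blood pressure monitoring and lifestyle modifications". Section 5.2 stratifies randomisation by site. Section 6.1 states that "the effective sample size of 264 subjects will provide 90% power" for a mean difference of about 0.4 SD; it gives no power for a categorical outcome.

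**The concern.** The plan treats the two kinds of Aim 2 outcome unequally. A continuous outcome is compared with its baseline value in the model. The categorical outcome is compared by a test that has no place for a covariate, and the text does not say how a change from baseline in a category would be tabulated.

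If the categories are ordered, more is lost. Fisher's test on a table with three or more columns asks only whether the two distributions differ. Moving participants from never to daily and moving them from daily to never are the same kind of evidence to it. A small p-value would then not establish the hypothesised increase, and there would be no single estimate of its size. A moderate real shift would also be detected less often than by a test that uses the order.

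**Working it through.** **1. The plan's own figure.** Inputs from Section 6.1: effective N of 264, hence 132 per arm, and a difference of 0.4 SD. Alpha for Aim 2 is not stated; two-sided 0.05 is assumed.

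Power = Φ(d·√(n/2) − z) = Φ(0.4 × √66 − 1.960) = Φ(3.250 − 1.960) = Φ(1.290) = 0.901.

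This reproduces the stated 90%. With alpha 0.025 the result would be Φ(3.250 − 2.241) = 0.843, so 0.05 is the level that fits. (A 15% dropout from 340 leaves 340 × 0.85 = 289, not 264. That is a separate matter; 264 is kept here because the plan's power rests on it.)

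**2. Which variable.** Weight and BMI are numeric, and dietary intake such as sodium is naturally so. That leaves monitoring frequency as the most plausible categorical outcome. Activity could also be banded, and monitoring frequency could be a count, so this is an inference.

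**3. What holds for any coding.** Fisher's test conditions on the table margins and accepts no baseline or site term. At most it is accompanied by an unadjusted odds ratio, and only in the 2×2 case.

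**4. Three or more ordered categories (assumed).** Usual care follows a standard normal variable cut into k categories. The intervention arm is shifted by 0.4 SD, with 132 per arm and alpha 0.05. The Fisher test in its r×c form (Monte Carlo p-values) was compared with the Wilcoxon rank-sum test over 1,200 runs per setting.

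| Usual-care distribution | Fisher | Wilcoxon | Loss (points) |
|---|---|---|---|
| 3 equal | 0.72 | 0.82 | 10 |
| 4 equal | 0.71 | 0.85 | 13 |
| 4 skewed (60/20/12/8%) | 0.65 | 0.82 | 17 |
| 5 equal | 0.68 | 0.86 | 18 |
| 5 skewed (50/20/12/10/8%) | 0.67 | 0.84 | 17 |
| 6 equal | 0.64 | 0.86 | 22 |
| 6 skewed (45/20/13/10/7/5%) | 0.61 | 0.85 | 24 |

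Losses are taken before rounding. The Monte Carlo standard error of a power near 0.67 is √(0.67 × 0.33 / 1200) ≈ 0.014.

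The mechanism is the degrees of freedom. A 0.4 SD shift carries a noncentrality of 0.4² × 66 = 10.56. Spread over 1, 2, 3, 4 or 5 degrees of freedom, a chi-square test has power 0.90, 0.84, 0.79, 0.74 or 0.71. The table also includes the information lost by grouping, which affects both tests.

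**5. A large contrast.** With a 0.8 SD shift (500 runs per setting), both tests have power of at least 0.998 in every setting. There is no loss.

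**6. A binary outcome.** There is no order to ignore, and the two proportions show the direction. By exact enumeration, the same 0.4 SD shift gives Fisher power of:
- 0.48 for 10% against 18.9%
- 0.62 for 20% against 32.9%
- 0.67 for 30% against 45.0%
- 0.69 for 50% against 65.5%
- 0.60 for 70% against 82.2%

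The shortfall from 90% comes mainly from dichotomising: a pooled z-test reaches only 0.54, 0.67, 0.72, 0.73 and 0.65. For an assumed 30% against 60%, Fisher power is 0.998.

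**The case against.** The strongest reply is that the documents do not show the outcome to be ordinal. No scale is given. Section 5.4 has staff review the readings stored on the intervention arm's monitors, so frequency might be a count, and Section 6.2 would then already assign a Wilcoxon test or ANCOVA. The weekly measuring target given to the intervention arm would equally suit a yes/no coding. The missing appendix may settle the coding, the effect measure and the adjustment. This stands, and it makes the ordering and direction points conditional.

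Secondly, the mixed-effects models would use baseline measurements and give signed estimates. A reader might infer that Aim 2 as a whole ignores baseline and says nothing about direction; the documents do not support that. The tabulated variable might even be a category of change. But the models are planned to describe the data over time, and the group comparison named for the categorical variable is still Fisher's test.

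Thirdly, the contrast may be large. Only the intervention arm receives a monitor, is asked to use it regularly and discusses it on each of 12 calls, so the power loss may be nil. Section 5.3 does say that all patients would be encouraged to monitor at home, so a large contrast is not assured. The lack of adjustment does not depend on the size of the contrast.

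On site, the Aim 1 ANCOVA in the Study Summary names only arm and baseline. The omission of site is therefore not peculiar to the categorical outcome.

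**Conclusion.** The point holds as a modest, cheap improvement to one secondary comparison. It does not touch the co-primary blood pressure analyses. Without any assumption about coding, the named test cannot adjust for baseline or for the stratification factor and gives no adjusted effect estimate. If the outcome has three or more ordered categories, it also discards the order and does not by itself demonstrate an increase.

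The power cost is 10 to 24 points against a rank test. It rests on assumed category counts and distributions, 132 per arm, two-sided alpha 0.05 and a 0.4 SD shift, and it vanishes near 0.8 SD.

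Two stronger readings should be resisted. One is that the plan loses about 20 points of power outright: that describes particular five- or six-category scenarios at a moderate effect, and no such categories or effect sizes for this outcome appear in the documents. The other is that real effects will be missed at 12 months once coaching has ended: Section 6.2 attaches Fisher's test to the 6-month comparison only, and frames 12 months as maintenance of differences already seen.

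**What to change.** Name the categorical variable in Section 6.2 and the SAP and state its coding. Make the 6-month comparison a regression on arm, baseline category and site:

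- **Ordinal:** a proportional-odds model reporting the common odds ratio with 95% CI, with a site-stratified Wilcoxon test as the check if proportional odds is doubtful.
- **Binary:** logistic regression with the same terms, reporting the odds ratio with 95% CI.

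The cost is SAP wording, settled before unblinded analysis. No new data are needed, provided the baseline category is collected, as a change endpoint in Section 3.1.2 requires. The drawback is the proportional-odds assumption in the ordinal case. The odds ratio will also be conditional on baseline and site and should be labelled so. One further gain is that a log odds ratio with its standard error can be pooled across the multiple imputations planned in Section 6.2, which a Fisher p-value does not directly allow.
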